- Aim 2 (Survey): Nurses will be eligible for survey administration if they worked >50% time on one study nursing unit during a 6-month study period; this will ensure adequate exposure to the study conditions and the opportunity to complete baseline and follow-up surveys. About 1,980 nurses will be eligible.
- Qualitative analysis of implementation: Nurse unit managers and nurses will be eligible for the qualitative interview if they worked at least 50% time on the study nursing units for the entire duration of a SAFE Loop implementation period. (We will enroll 32 participants out of a pool of approximately 800 eligible nurses.)

Patients:

Cedars-Sinai has a total of 294,470 patient-days of care in eligible nursing units per year. Patients located in experimental and control group nursing units will be eligible for participation. If patients transfer between nursing units during the study, analyses will allocate each day of the hospitalization to the unit where the patient was that day. For the review of medical records under Aim 3, we will randomly select 1,520 patients hospitalized during the baseline and follow-on periods.

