6.3 MEASURES TO MINIMIZE BIAS: RANDOMIZATION AND BLINDING

Random Sequence Generation, Allocation Concealment, and Blinding: A researcher (not on the SAFE Loop or Data Collection teams) will use computer-generated random numbers to randomly assign the 4 nursing units within each of the 5 randomization blocks to one of 4 study groups, reflecting 2 arms (intervention and control) and 2 periods of time (sequential implementation; see Table below). Next, the researchers will place lists of the nursing units assigned to each group in opaque, sealed envelopes labeled with group numbers. At the start of each implementation period, the SAFE Loop Team will open the corresponding envelopes to determine the 5 nursing units that are assigned to each group. Research staff involved in data collection will be blinded to which nurses and patients are assigned to which arm.

Table: Study Design, Including Study Arms and Measurement Periods								
Group	½ Year 1		Year 2			Year 3		
1	Baseline	b	SAFE Loop	f	i	Follow-on		
2	Baseline	b	Control	f		Follow-on		
3			Baseline	b	SAFE Loop	f	i	Follow-on
4			Baseline	b	Control	f	Follow-on	
Light green = baseline measurement periods for Aims 1 & 3								
Orange = baseline (b) and follow-up (f) survey deployments for Aim 2								
Dark blue = SAFE Loop arm								
Medium blue = control arm								
Yellow = qualitative interviews (i) on implementation and follow-on period								
Dark green = follow-on period for Aim 3								

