Non-intercepted (NCC MERP C-D)	A medication error in which the patient received the medication but did not to experience harm.	A patient with a known allergy to an antibiotic receives the drug anyway but does not develop a rash.

*An injury is an unintended consequence of care that negatively affects a patient's health and/or quality of life. † A medication error is an error anywhere in the process of drug ordering, dispensing, administration, and monitoring.

Descriptive Measures: We will characterize event severity/harm (NCC MERP categories), medication class (e.g., cardiovascular, diabetes, etc.), and route of administration (intravenous, oral, etc.). We will classify any errors by stage in drug therapy (ordering, dispensing, administering, monitoring), profession(s) involved (physician, pharmacist, nurse, other), and error types (allergy, drug-disease interaction, drug-drug interaction, drug-lab interaction, duplicate therapy, therapeutic omission, concentration, duration, route/dosage form, dose/frequency/rate, wrong medication, wrong patient, wrong timing, incomplete order).^{5,6,38,61} We will assess which events are Target Medication Events used by Group 1 and 3 nursing units (yes, no; and which unit).

B. Data Collection: The nursing units will implement mitigation plans designed to prevent Target Medication Events toward the end of the SAFE Loop implementation (Section 2B), which means that medication events will not start to fall until after that. Accordingly, we will monitor medication events during a baseline period, the implementation period, and 6-month follow-on period after implementation (Section 3A). To identify medication events, we will randomly sample 1,520 hospitalizations divided equally between the four study groups and the baseline and follow-on periods. (We will exclude the emergency department from Aim 3).

To detect medication events, we will employ the widely accepted Trigger Tool Method by Institute for Healthcare Improvement. It involves two stages: (1) nurses systematically screen medical records for “triggers” (clues that an event occurred) and write synopses of possible events, and (2) physicians review synopses to confirm and classify them. Many studies have used these methods, including studies by Dr. **[name]**.^{5,6,38,61-64}

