Screening: Research nurses will search for several types of triggers including the use of medications that can counteract other medications (e.g., naloxone), abnormal lab results (e.g., serum glucose <50 mg/dL), clinical events (e.g., rash), abrupt cessations of medication, and transfers to a higher level of care.⁵² To increase our ability to detect potential ADEs, we will add an additional “trigger”: events in the Cedars-Sinai “Ivents” database, where pharmacists routinely record changes to medication therapy made to reduce the risk of harm (overseen by Dr. **[name]**). Ivents reports are distinct from voluntary incident reports (we will not include regular incident reports). Two research nurses will perform these screenings, blinded to study arm. To train the nurses, we will adapt training manuals and procedures from the Institute for Healthcare Improvement and our prior research.^{5,6,52} Manuals will include descriptions of the Trigger Tool method, Ivents reports, and variables employed in classifying the medication events. Through a 3-day in-person training session, nurses will become familiar with the manuals, ask questions, review 3 sample charts with supervision (by [name]), review an additional 5 to 7 sample charts independently, and then meet with the trainer to assess proficiency. During data collection, quality monitoring and training reinforcement will occur in two ways (1) the research nurses will submit questions and maintain a log of trainers’ responses, and (2) physician reviewers will ask for clarifications when the event synopses lack essential information. To obtain potential covariates for use in regression models, nurses will also extract patient age, gender, race, ethnicity, discharge diagnosis codes needed to score the Elixhauser comorbidity index, and primary and secondary payer. To ascertain reliability (Cohen’s kappa statistics), a randomly chosen 10% of medical records will undergo duplicate review.

Classification: Two physicians will independently review each synopsis, employing a standardized rating form that includes the variables above. Next, they will meet to discuss responses. When there are discrepancies, physicians may ask the research nurses for additional information or involve a third physician to break ties. To ensure blinding, synopses will not include identities of patients, clinicians, or

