9.4.2 ANALYSIS OF THE PRIMARY EFFICACY ENDPOINT(S)

Aim 1 Analyses:

Descriptive Analysis: We will perform descriptive analyses of reporting practices during the baseline periods and intervention periods, stratified by study arm. We will calculate rates of reported Target Medication Events and total reported medication events per 1000 patient-days (# of reports*1000/# of patient-days). Next, we will calculate the percentages of reported incidents in each NCC MERP category and the percentages of reports for which preventability could be determined. Finally, we will calculate

the number of contributing system, human, and patient factors per report and describe the types of factors reported.

Statistical Analyses: We will compare changes over time between study arms for: (a) rate of incident reports per 1000 patient-days, and (b) number of system plus human factors per report. Multivariable Poisson regression models will be fitted with response variables as (a) number of reports per patient, with offset given by the length of stay divided by 1000; and (b) number of system plus human factors per report. For both models, the main hypothesis is whether there is an interaction between study arm and time period (baseline, post-intervention). Nursing units will be divided between two implementation steps, creating the possibility of an implementation trend. Therefore, a three-way interaction among study arm, time period, and implementation step (Step 1: Group 1 and 2, Step 2: Group 3 and 4) will be tested. If this is statistically significant, results will be presented separately for each implementation step. Otherwise, implementation step will be an additive effect. Random effects will describe nursing units and models will adjust for demographics, Elixhauser comorbidity index, and primary payer (collected under Aim 3). All hypotheses will be two-sided at 5% significance level. Calculations will be performed in R-package, version 3.5.3.

Aim 2 Analyses:

Descriptive Analysis: We will calculate survey response rates, examine respondent characteristics (years worked in current profession, hospital, and current nursing unit and hours worked per week), and describe outcome measures (overall scores and composite measures) during each study period, stratified by study arm.

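### The Aim 1 models, including primary outcome H1.2, take their patient covariates from Aim 3, whose chart sample covers only about 3% of hospitalizations, none allocated to the implementation period and none from the emergency department

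*Combined protocol and SAP*

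**What the plan says.** Section 9.4.2 (Aim 1, Statistical Analyses) fits two Poisson models: reports per patient with a length-of-stay offset (H1.1), and contributing factors per report (H1.2, the Aim 1 primary outcome in Sections 3 and 9.1). The main hypothesis in each is the arm-by-period interaction, with periods labelled baseline and post-intervention. Of the covariates it says "models will adjust for demographics, Elixhauser comorbidity index, and primary payer (collected under Aim 3".

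Section 8.1 shows how Aim 3 obtains them. During chart screening, "To obtain potential covariates for use in regression models, nurses will also extract patient age, gender, race, ethnicity, discharge diagnosis codes", together with payer. The charts are a sample: "we will randomly sample 1,520 hospitalizations divided equally between the four study groups and the baseline and follow-on periods". Section 5.1 agrees: "we will randomly select 1,520 patients hospitalized during the baseline and follow-on periods". Section 8.1 adds: "We will exclude the emergency department from Aim 3".

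Aim 1 appears to use other periods. Its descriptive analysis in Section 9.4.2 covers "reporting practices during the baseline periods and intervention periods", and the legend to the design table in Section 6.3 reads "Dark green = follow-on period for Aim 3".

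**The concern.** The covariates are said to come from a data set that was not drawn to match the rows of the Aim 1 models. Aim 3 is a small random sample from two periods. Aim 1 uses all medication incident reports and, for the rate model, all patients on the units, including those with no report. If the plan were followed as written and only rows with covariates were used, nearly all Aim 1 data would drop out, including a primary outcome. If it is not followed as written, someone must pick another source and decide what to do with reports that have no covariates, and the plan does not say how. Those decisions would be made with outcome data in hand.

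**Working it through.** **The plan's own figures (Section 9.2).** 294,470/20/2 = 7,361.75 patient-days and 665/20/2 = 16.625 reports per unit and 6-month period; 665/294.470 = 2.258 reports per 1,000 patient-days. These match the stated 7,362, 16.6 and 2.26. Table 1 follows from the standard cluster-trial formula for rates, solved for d = λ1 − λ0:

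c = 1 + (1.960 + 0.842)² × [(λ0 + λ1)/y + k²(λ0² + λ1²)] / d²

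Here c is 10 units per arm (5 with an implementation trend), y is the exposure per unit-period and k is the between-cluster coefficient of variation. For H1.2, λ0 = 0.70, y = 16.625, k = 0.01 and d = 0.299 give 1 + 7.849 × 0.10234/0.08940 = 9.98, or 10 units as required. All 16 entries of Table 1 reproduce within 0.2%. So Table 1 counts every one of the 16.6 reports per unit-period and allows for none lost to missing covariates.

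**Charts.** 1,520/(4 groups × 2 periods) = 190 per group-period, so 4 × 190 = 760 at baseline and 760 in follow-on. The sampling sentence leaves 0 for implementation.

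**Coverage of one period.** The synopsis (Section 1.1) gives 49,000 inpatient and 7,700 observation encounters a year, hospital-wide.
- Inpatient plus observation: 56,700/2 = 28,350, and 760/28,350 = 2.7%.
- Inpatient only: 49,000/2 = 24,500, and 760/24,500 = 3.1%.

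The study-unit share of these totals is not given. If it were only half (an assumption), coverage would double to 5.4% to 6.2%. If transfers meant that nearly all stays in both steps' baseline half-years counted, it would halve to 1.3% to 1.6%. The conclusion is the same throughout.

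**Reports.** About 665/2 = 332.5 are expected at baseline. Leaving out the ED in proportion to patient-days gives 332.5 × 275,362/294,470 = 310.9. At 2.7% to 3.1% coverage, about 8 to 10 of these would fall on sampled charts, if reported stays are as likely to be sampled as others.

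**ED.** It is one of the 20 randomized units, with 19,108/294,470 = 6.5% of patient-days and no sampled stays.

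**Readings of post-intervention.**
- Intervention period: 0 allocated charts. With baseline rows only, period does not vary, so the adjusted arm-by-period interaction cannot be estimated from the allocated charts alone.
- Follow-on: 760 charts. The interaction can be estimated, but on 2.7% to 3.1% of stays.
- Both together: 760 charts over two half-years, 760/56,700 = 1.3% to 760/49,000 = 1.6%.

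**The case against.** The strongest reply is that a wider source is plainly intended. The table in Section 2.3.1 lists extraction of electronic health record variables (row 6) separately from chart review (row 4), with study IDs for linkage. Section 7.3 expects complete data on all patients, and the rate model could never have run on 1,520 charts. This stands as evidence that the gap can be filled. A reader might infer that the H1.2 model cannot be fitted, or that Table 1 is invalid; the documents do not support that. No text restricts the models to rows with covariates, unadjusted models are unaffected, and the covariate list is already fixed, which limits the analyst's freedom. But no text ties row 6 to Aim 1, its periods or these variables, and the incident-report data elements in Section 10.1.9.1 do not include them.

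A reader might also take the absence of intervention-period data as settled. It is not. Section 9.4.2 does not define post-intervention. The synopsis expects reports on about 1,663 patients under Aim 1, which equals 665 × 2.5 years, the whole span of the design table; two 6-month periods would give 665. Section 8.1 also says events will be monitored during implementation, although its sampling sentence gives that period no charts. And because "analyses will allocate each day of the hospitalization to the unit where the patient was that day" and the two steps appear to overlap in time, a few intervention-period reports could be reached through transfers. The documents give no transfer rate, so that number cannot be estimated.

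Finally, the plan does have a missing-data method: multiple imputation in Section 9.2. It sits under Aim 2, beside the survey power calculation. Section 10.1.9.1 refers missing data back to the assessment teams, which is data cleaning rather than an analysis rule.

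**Conclusion.** The stated covariate source for Aim 1 is wrong as written. It would leave roughly 97% of Aim 1 patients and reports without covariates, and all ED stays as such, under any reading of post-intervention. That percentage rests on hospital-wide encounter totals, a 6-month baseline and groups of similar size; plausible departures leave coverage between about 1% and 6%. The further conclusion, that the adjusted interaction could not be estimated, holds only if post-intervention means the intervention period and only for the allocated charts used alone. Section 9.4.2's descriptive text and the Section 6.3 legend favour that reading without settling it. This is a specification error in the analysis of a primary outcome. It does not show that the data cannot be obtained, and it should be corrected before Aim 1 outcomes are analysed.

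**What to change.** In Section 9.4.2:
- Replace the reference to Aim 3 as the covariate source with the record extraction in row 6 of the Section 2.3.1 table, linked by study ID. It should cover all patients on the 20 units, ED included, in both Aim 1 periods, and name demographics, Elixhauser index and primary payer.
- State which period post-intervention means for Aim 1. Reconcile this with the 1,663 in the synopsis, and reconcile the implementation-period monitoring in Section 8.1 with its chart allocation.
- State that reports without linked covariates stay in the H1.2 analysis, and how. Some reports will have no patient at all: severity category A in Table 6 is a hazard that involved none, and Section 6.1.1 trains intervention nurses to focus on unsafe conditions, so dropping such reports could affect the arms unequally.

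The cost is a few sentences, a larger extract from records the hospital already holds, and a linkage list that goes beyond the incident-report patients for whom Section 10.1.9.1 now creates it. Case-mix adjustment is kept, and no second candidate primary model is needed.

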The survey takes 10-15 minutes to complete and includes 42 items used to derive 12 composite measures (**Table 8**), 2 single-item measures, and respondents' backgrounds (unit, staff position, interaction with patients, years of experience in current profession, hospital, and current nursing unit). Most items are scored on a scale from 1 (strongly agree) to 5 (strongly disagree). Creating composite scores involves: (1) inverting the scales of any negatively worded items, (2) identifying positive responses (1 or 2); (3) calculating the percent of responses that were positive for each item (excluding missing values), and (4) averaging the percent positive across all items within a composite measure.

The two composite measures we plan to use are directly relevant to incident reporting and likely to be responsive to system-level changes. *Feedback and Communication About Error* includes three items: staff are informed about errors, discuss ways to prevent errors, and are given feedback about changes implemented. The *Frequency of Events Reported* also includes three items: staff report mistakes that are caught before affecting the patient, with no potential to harm, and that could harm but did not. In a prior analysis from three nursing units at three different hospitals, scores on these two composite measures were correlated ($\rho=0.56$) but factor analyses indicated that they captured distinct concepts (loaded separately). Respectively, Cronbach α values for these measures were 0.77 and 0.78 among nurses, demonstrating good internal consistency.⁵⁵

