B. Data Collection: Cedars-Sinai routinely surveys staff every two years using the Hospital SOPS. For the study, we will survey ~1980 eligible nurses on study nursing units twice via 4 total deployments of the full Hospital SOPS during two-week intermissions between study periods (Section 3A). To identify eligible nurses, we will obtain staffing databases including names, email addresses, title/position, percent effort, dates of work on the unit, and work schedule. At least 85% of nurses on study units will be eligible. Two weeks before deployment, we will send email notices to expect the survey and a researcher will visit nursing units to reinforce survey completion. The survey will be delivered via REDCap using a weblink embedded in an email. During each deployment, we will deliver the survey three times. We will incentivize completion at the individual (lotteries for iPads) and unit levels (gift baskets of snacks for response rates >65%). To minimize detection bias, the survey will not refer to the SAFE Loop intervention. To avoid having incomplete outcome data, we will monitor survey response rates and make adjustments to procedures as needed.

Methods for Aim 3: Rates of Target Medication Events

A. Measures: The primary outcome will be the *rate per 1,000 patient-days of Target Medication Events (preventable plus potential adverse drug events)* selected by the 10 nursing units in Groups 1 and 3. We will also examine the rate of events involving harm. We will define events as in prior research (**Table 10**).^{38,61,62}

Table 10: Medication Event Definitions		Examples
ADE (NCC MERP severity E-I)	A patient injury* resulting from a medical intervention related to drug(s).	A rash due to an antibiotic.
Preventable	An adverse drug event due to a medication error. †	A rash due to an antibiotic given despite known allergy.
Non-preventable	An adverse drug event not due to an error.	A rash occurring after first exposure to an antibiotic.
Potential ADE	A medication error that had the potential to cause injury but did not.	
Intercepted (NCC MERP B)	A medication error that was detected and stopped before the patient received the medication.	A pharmacist filling orders discovers a known allergy and prompts the prescriber to switch antibiotics.

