Power calculations are the same for both composite outcome measures. The baseline percentages of positive responses are 75% (H2.1) and 72% (H2.2). We assume 85% of 1980 nurses will be eligible and a 60% response rate (50.5 responses per nursing unit per deployment). We also assume a discrete uniform distribution for each composite measure with only four possible values (0%, 33%, 66%, 100%) per nurse because each measure contains 3 items. Therefore, we assume standard deviation (SD) equal to 37%, and a between-cluster coefficient of variation of 0.65 as recommended by Campbell and Walters.² The **Table** presents the minimum detectable difference in the percentage of positive responses as a function of the intra-cluster correlation (ICC) and presence of implementation trend, using a two-sided t-test for Normal means with 80% power at 5% significance level. Based on prior studies, a meaningful difference in the percentage of positive responses is 8.6 percentage points (pp).³ Missing data patterns will be examined using the method proposed by Little⁴ if the data is found to be not missing at completely random, missing values will be imputed with values drawn from fully conditional specifications using the multivariate imputation by chained equations (MICE) algorithm,^{5,6} with the number of imputed datasets chosen such that the maximum loss of efficiency of 5%.⁷ The plausibility of imputed values will be checked by corresponding diagnostics. The outlined statistical analysis will be performed for each imputed dataset and results will be pooled. All hypotheses will be two-sided at 5% significance level. Calculations will be performed using R-package, version 3.5.3.

Implementation trend	Intra-cluster Correlation			
	0.01	0.05	0.10	0.20
Yes	10pp*	11pp	12pp	13pp
No	7pp	8pp	10pp	11pp

¹ [name] TK, Bell DS, Paddock SM, Hilborne LH. Contributing factors identified by hospital incident report narratives. Qual Saf Health Care. Oct 2008;17(5):368-372.

² Campbell MJ, Walters SJ. How to design, analyse and report cluster randomised trials in medicine and health related research. John Wiley & Sons; 2014.

³ Campione J, Famolaro T. Promising Practices for Improving Hospital Patient Safety Culture. Jt Comm J Qual Patient Saf. Jan 2018;44(1):23-32.

⁴ Little RJ. A test of missing completely at random for multivariate data with missing values. Journal of the American Statistical Association. 1988;83(404):1198-1202.

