Assessment of Survey Measurement Properties: To evaluate the two selected composite measures' internal consistency, we will calculate Cronbach's α using data from baseline survey. To assess construct validity and convergent validity, respectively, we will evaluate associations (Pearson correlation coefficients) between scores on the composite measures and: (1) the full Hospital SOPS, and (2) incident reporting rates at the nursing unit level. To assess responsiveness, we will compare scores from baseline and follow-up surveys among nurses in the SAFE Loop arm (paired t-tests). If the composite measures do not demonstrate good internal consistency, construct, and convergent validity, we will use the full Hospital SOPS.

Statistical Analyses: We will compare changes over time between study arms for Feedback and Communication About Error and Frequency of Events Reported. Multivariable Normal regression models will be fitted for both endpoints and we will test hypotheses similarly to Aim 1. We will adjust for nurse characteristics from the AHRQ survey: years working in this hospital, years worked in current nursing unit, and hours worked per week. We will perform subgroup analyses by years of experience in current profession, because experience has been associated with medication error rates.⁵⁹

Aim 3 Analyses:

Descriptive Analysis: We will calculate rates of preventable ADEs and potential ADEs per 1,000 patient-days, both overall and for the Target Medication Events for the Group 1 and 3 nursing units. We will describe the severity of the events, medication classes, errors, clinicians involved, and stages in drug therapy.

Statistical Analysis: We will compare changes over time between study arms for rates of (a) Target Medication Events per 1000 patient-days and (b) harmful Target Medication Events per 1000 patient-days. Multivariable Poisson models will be fitted with response variable as the number of (a) target medication events and (b) harmful medication events, with offset the length of stay divided by 1000

days. We will test hypotheses similarly to under Aim 1. Model covariates will include patient demographics, biological sex, Elixhauser comorbidity index, and insurance payer.

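### The Aim 2 construct-validity check correlates each composite with a survey total that contains its own three items, so the correlation is inflated towards keeping the composite (minor)

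*Combined protocol and SAP*

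**What the plan says.** Section 9.4.2 (Aim 2, measurement properties) sets three checks: Cronbach's alpha on baseline data for internal consistency, one correlation for construct validity, and one with unit-level reporting rates for convergent validity. For construct validity, "we will evaluate associations (Pearson correlation coefficients) between scores on the composite measures and: (1) the full Hospital SOPS". The consequence follows: "If the composite measures do not demonstrate good internal consistency, construct, and convergent validity, we will use the full Hospital SOPS".

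Section 8.1 shows the overlap. The survey "includes 42 items used to derive 12 composite measures", and its table of composites lists both Aim 2 measures among the 12. Feedback and Communication About Error "includes three items: staff are informed about errors" and two others. Frequency of Events Reported "also includes three items: staff report mistakes that are caught before affecting the patient" and two others. The study fields "4 total deployments of the full Hospital SOPS", so these items are inside the total.

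The document gives no rule for forming a full-survey score and no correlation or p-value that counts as *good*. It is also unclear whether the construct-validity correlation is taken across nurses or across units.

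**The concern.** The check is meant to show that a composite relates to the wider safety-culture construct. Correlating a part with a whole that contains it gives a positive value even when the part has nothing to do with the remainder. Zero is then not the reference value for no construct validity, and any observed r overstates the relation to the rest of the survey.

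The check helps decide whether the Aim 2 primary outcome (H2.1) stays in place. The overlap acts in one direction only, towards keeping the composite. At stake are the validity result that will be reported and the soundness of the switch rule.

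**Working it through.** **Inputs from the document.** 42 items, 12 composites, 3 items in each Aim 2 composite, correlation 0.56 between those two composites in prior data, alpha 0.77 and 0.78 (8.1); 1,980 nurses, 85% eligible, 60% response, composite scored "with only four possible values (0%, 33%, 66%, 100%) per nurse because each measure contains 3 items" (9.2); 20 units (9.3).

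**Reproducing the plan's figures.** 1980 × 0.85 × 0.60 / 20 = 50.49 responses per unit, against 50.5 stated. Over 20 units this is 1,009.8, about 1,010 baseline respondents. The SD of a discrete uniform on the four values is 37.2 to 37.3, against 37% stated.

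**Model (assumed).** The full score is the mean of 12 equal-variance composites. The tested composite correlates c with each of the other 11, which correlate rho with one another. Then

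- r(full) = (1 + 11c) / √(12 + 110·rho + 22c), own items included;
- r(rest) = 11c / √(11 + 110·rho), own items removed.

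Chances below use Fisher's z with SE 1/√(n − 3), treating observations as independent.

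**Unrelated composite (c = 0).** r(rest) = 0 and r(full) = 1/√(12 + 110·rho). For rho = 0.56: 1/√73.6 = 0.117; z = 0.117 × √1007 = 3.72; chance of p < 0.05 = Φ(3.72 − 1.96) = 96%.

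| rho | r(full) | p < 0.05, n = 1,010 | r ≥ 0.3, n = 1,010 | p < 0.05, n = 20 |
|---|---|---|---|---|
| 0 | 0.289 | 100% | 35% | 23% |
| 0.1 | 0.209 | 100% | 0.1% | 14% |
| 0.2 | 0.171 | 100% | 0% | 11% |
| 0.4 | 0.134 | 99% | 0% | 9% |
| 0.56 | 0.117 | 96% | 0% | 8% |
| 0.7 | 0.106 | 92% | 0% | 7% |

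Item-level simulation at n = 1,010 agrees: significant in 96% to 100% of runs, and r ≥ 0.3 in 43% at rho = 0 and in none at rho of 0.3 or more. With own items removed, mean r is 0.00, the 5% test rejects in about 4% to 7%, and r ≥ 0.3 never occurs.

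*If the full score is instead the mean of 42 items:* r = √(V3/(V3 + V39)), with V3 = 3 + 6·α/(3 − 2α) and V39 = 39 + 39·38·q, where q is an assumed inter-item correlation. For q from 0.05 to 0.40, r runs from about 0.23 down to 0.10, and p < 0.05 occurs in 88% to 100%.

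**Related composite, n = 1,010.**

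| rho | c | r(rest) | r(full) | Cut-off | Passes, own items removed | Passes as planned |
|---|---|---|---|---|---|---|
| 0.4 | 0.15 | 0.22 | 0.34 | 0.3 | 0.4% | 94% |
| 0.56 | 0.20 | 0.26 | 0.36 | 0.3 | 7.5% | 99% |
| 0.4 | 0.30 | 0.45 | 0.54 | 0.5 | 1% | 97% |

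Over rho 0.2 to 0.56 and c 0.10 to 0.30 the inflation is 0.09 to 0.16.

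**All 12 composites equally correlated (c = rho).** r(full) = √((1 + 11·rho)/12).

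| rho | r(full) | r(rest) | Inflation |
|---|---|---|---|
| 0.2 | 0.52 | 0.38 | 0.13 |
| 0.3 | 0.60 | 0.50 | 0.10 |
| 0.56 | 0.77 | 0.72 | 0.05 |

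**The case against.** A reader might infer that this check cannot fail, or that its result carries no information. The document does not support that. Near-certain passing requires that *good* mean p < 0.05 across about 1,010 nurses. Section 9.4.2 gives no such rule; the 5% level is stated for hypotheses, not for psychometric checks. An r of 0.11 to 0.29 need not be called good. With a cut-off of 0.3 an unrelated composite passes at most about 35% of the time by formula, and about 0% once the others correlate 0.1 or more. On 20 unit means it is significant in only about 7% to 23% of cases.

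The unrelated composite is also an extreme case. Section 8.1 reports a correlation of 0.56 between the two chosen composites, so neither is unrelated to everything else. If that value held throughout, the inflation would be only about 0.05.

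Two other conditions also govern the switch, and a wrong pass merely leaves in place the pre-specified primary outcome, which has prior support (alpha 0.77, separate factor loading). It does not bias the comparison between arms.

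All of this stands, and it makes the point minor. It does not remove the overlap. The other two checks measure different properties, and the plan has chosen to re-test the composites and tie the endpoint to the result. For a composite near a cut-off the shift can still decide the outcome.

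**Conclusion.** The concern holds as a minor point. The construct-validity correlation is inflated by item overlap, always towards retaining the composite: from 0 to about 0.11–0.29 for an unrelated composite, and by about 0.05–0.16 for related ones. Whether this changes a decision depends on a criterion that the plan does not state. Nurse-level significance would pass an unrelated composite in about 92–100% of data sets, whereas a cut-off of 0.3 or more, or a significance test on unit means, usually would not. Cut-offs of 0.3 or 0.5 can still be crossed wrongly by weakly or moderately related composites.

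What is affected is the reported validity and the rule for switching to the full survey, not the arm-by-period estimate. The sizes rest on an assumed full score (mean of 12 equal-variance composites), assumed correlations among composites (only the 0.56 is documented), and independent responses.

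**What to change.** In section 9.4.2, replace comparator (1) by: *the baseline Hospital SOPS score computed from the other 11 composites, excluding the items of the composite being assessed (corrected part-whole correlation)*. Apply it separately to Feedback and Communication About Error and to Frequency of Events Reported. State whether the correlation is across nurses or units, and what value counts as *good*, before the data are seen.

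The cost is a sentence or two in the SAP and a line of code, with no new data. The reported correlation will be somewhat lower than the uncorrected one.
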